## Abbreviations

cAMP	Cyclic adenosine monophosphate
CTCAE	Common Terminology Criteria for Adverse Events
DIET	Dyspigmentation, Induration, Erythema, and Telangiectasias
ERK	Extracellular signal-regulated kinase
hCG	Human chorionic gonadotropin
HRQOL	Health-related quality of life
LoSCAT	Localized Scleroderma Cutaneous Assessment Tool
MAPK	Mitogen-activated protein kinase
PDE-4	Phosphodiesterase-4
SDRC	Skin Disease Research Center (SDRC)
TGF $\beta$	Transforming growth factor beta

**1. Protocol Title:**  
Pilot Study Evaluating the Efficacy of a Topical PDE4 Inhibitor for Morphea

**2. Purpose of the Study:**  
To determine the clinical efficacy of crisaborole 2% ointment in the treatment of morphea. Specifically, to:

- a. Compare the difference in dermal thickness and fibrosis as measured by histology at baseline and after 12 weeks of crisaborole 2% ointment, applied 2 times a day.
- b. Compare changes in physician and patient reported outcomes at baseline, 4, 8 and 12 weeks of treatment.

**3. Background & Significance:**  
Morphea is an autoimmune fibrosing skin disorder of still unknown etiology. It can be associated with significant morbidity, and effective topical and systemic therapies are still lacking. cAMP is known have an anti-fibrotic effect in skin models as well as other organs. It is therefore not surprising that phosphodiesterase-4(PDE4), which degrades cAMP, has been implicated in the pathogenesis in both animal and human studies. Preclinical studies have suggested that PDE4 inhibition may attenuate the oxidative processes that mediate fibrosis. Systemic PDE4 inhibitors demonstrated anti-fibrotic effects in multiple murine skin fibrosis models, including the bleomycin-induced skin fibrosis models, the topoisomerase I mouse model and in murine sclerodermatous chronic graft-versus-host disease. This anti-fibrotic effect was mediated through the blockage of cytokines and other immune mediated mechanisms. Dermal fibroblasts and myofibroblasts in an inflammatory disease such as psoriasis have increased expression of PDE4. Furthermore, PDE4 inhibition reduced TGF $\beta$  mediated fibroblast migration and myofibroblast transformation.

PDE4 facilitates proinflammatory signals by degrading cAMP in inflammatory cells, smooth muscle cells, and keratinocytes. In mouse models, the anti-fibrotic effect of PDE4 inhibition was mediated though the blockage of cytokines and other immune mediated mechanisms. Keratinocytes play an active part in the modulation of inflammation in a variety of cutaneous inflammatory and immune disorders. Our group has a particular interest in the role of the keratinocyte mediated inflammation and biology. Cross talk exists between cAMP and the RAS/RAF/mitogen-activated protein kinase (MAPK) and extracellular signal-regulated kinase (MEK)/ERK pathway. MEK/ERK has been implicated in the development of fibrosis, and inhibition of this pathway interferes with the profibrotic response to TGF $\beta$ .

**4. Design & Procedures:**

A Phase 2, pilot, proof-of-concept, open label, single arm prospective study to assess the safety, tolerability and efficacy of using crisaborole 2% ointment for adult morphea. We will recruit 20 adult ( $\geq 18$  years of age) patients with morphea.

Patients will be recruited from the Duke University Dermatology Autoimmune Disease Clinic. In addition, patients will also be recruited from the entire Duke System, and from community and academic dermatology practices.

Patients will be identified by their physician, nurse, or other member of their clinical care team. Upon notification by the primary team, the study team will approach patients to discuss the study, treatment protocol, associated procedures and obtain informed consent. Patients who are referred from outside of Duke will have to obtain a Duke Medical Record Number (MRN).

**Treatment:**

Patients will be asked to apply crisaborole 2% ointment, twice daily, on affected plaques for 12 weeks.

Medication will be provided free of charge by Pfizer, as part of the grant that is funding this study. These will be dispensed by the study group at baseline and during the subsequent clinic visits.

**Skin punch biopsy of sentinel plaque:**

A sentinel plaque will be selected at baseline. A 4 mm skin punch biopsy will be performed at baseline and at 12 weeks, on the same affected plaque.

If a biopsy has been previously taken of the affected plaque and is available for review, this will be used as the baseline biopsy. Patients who drop out of the study because of progression of their disease or adverse effects will undergo a skin punch biopsy at the time of drop out.

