**Histologic and genomic assessment of skin biopsy specimen:**

Each biopsy specimen will be bisected. Half will be formalin fixed and sent for histologic evaluation. Histologic assessment will be performed by an experienced academic dermatopathologist, who will be blinded to the study design. This will be performed within the Duke Dermatology Skin Disease Research Center (SDRC).

Dermal thickness will be measured and compared before and at the end of treatment.

The other half will undergo processing for Nanostring gene expression analysis. Specimens will be sent to the Nanostring Core Facility at the University of North Carolina (UNC) , de-identified except for study subject number. Gene expression analysis is included for future research purposes only. A Material Transfer Agreement will be completed and executed between Duke and UNC. MTA will be fully executed and uploaded into eIRB prior to any samples being sent outside of Duke.

The Lineberger Cancer Center Translational Genomics Laboratory (TGL) at UNC provides an assortment of analysis services employing the Nanostring™ nCounter platform. These include gene expression, miRNA expression and miRNA gene expression copy number variation analysis, single gene expression, lncRNA expression, Chip-String and RNA-Protein profiling. Nanostring™ supplies custom and off-the-shelf assays for various groups of target genes including immunology, inflammation, and pan cancer panels offering pathway, immune and progression profiling. TGL maintains 2 nCounter Prep Stations which can process 12 post-hybridization samples every 3 hours. A generation 2 nCounter digital analyzer can sequentially scan up to 6 cartridges of 12 samples each with a maximum resolution scan requiring approximately 5 hours per

[figure not shown]
cartridge. Data is provided to the client electronically for analysis using the NSolver v. 3.0 software provided by Nanostring™. LCCC Bioinformatics can also provide Nano Nanostring™ string analysis services. TGL employs 4 trained specialists experienced in assorted types of Nanostring™ assays.

All sample information and metrics are recorded and maintained in the gPATH Lab Information Management System (LIMS) designed and maintained by LCCC Bioinformatics.

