#### **Clinical assessment**

Patients will have a clinical assessment at baseline and at weeks 4, 8 and 12. After week 12, patients who need further treatment will undergo standard of care treatment as determined by their primary dermatologist. An optional post treatment follow-up will be performed at week 20.

Physician and patient reported assessment and skin imaging will be performed at baseline, week 4, 8 and 12, and at week 20. Photography will also be performed at baseline and week 12.

Physician assessment will utilize two previously described and validated scoring metrics. The sentinel plaque will be evaluated using Dyspigmentation, Induration, Erythema, and Telangiectasias (DIET) score. Overall disease severity will be evaluated using the Localized Scleroderma Cutaneous Assessment Tool (LoSCAT).

Health-related quality of life (HRQOL) will be measured using Skindex-29 which has previously been applied to morphea, and has a pruritus component.

Photographs will be taken using a standardized clinic camera.

B-Mode ultrasonographic imaging will be utilized to measure dermal thickness of the sentinel plaque at baseline, week 4, 8 and 12 and post-treatment at week 20.

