## Summary of Clinical Trial Design

	Baseline	Week 4	Week 8	Week 12	Week 16	Week 20
Crisaborole 2% ointment twice daily	x	x	x	x		
Clinic visit	x	x	x	x		x
LoSCAT scoring	x	x	x	x		x
DIET scoring	x	x	x	x		x
Skin punch biopsy	x			x		
Urine HCG	x	x	x	x		
Skindex 29	x	x	x	x		x
Skin imaging (ultrasound)	x	x	x	x		x
Photography	x			x		x

**Primary outcome measure** is the change in dermal thickness on skin biopsy at 12 weeks.

**Secondary outcome measures** are the following:

- Change in DIET score of sentinel plaque at 4, 8 and 12 weeks.

- Change in LoSCAT score at 4, 8 and 12 weeks.
- Skindex-29 at 4, 8 and 12 weeks.
- Change in dermal thickness of sentinel plaque by ultrasonography at 4, 8 and 12 weeks

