**10. Risk/Benefit Assessment and Safety Considerations:**

If a subject agrees to take part in this study, there may not be a direct medical benefit to them. The subject's morphea may improve from using the investigational drug in this study. It is also possible that a subject's condition will not improve on the investigational drug.

The pharmacokinetics of crisaborole as a topical medication have previously been studied. Crisaborole is metabolized to inactive metabolites upon absorption, making it both a safe option for therapy even in relatively extensive disease. There was minimal systemic effect of crisaborole ointment when applied twice daily for 28 days, over up to 35% body surface area, in children 2-17 years of age. Long term studies in adults and children with mild to moderate atopic dermatitis for as long as 48 weeks have also shown a low frequency of side effects. The most frequently reported treatment-related AEs (overall, 10.2%) were worsening of pre-existing atopic dermatitis (3.1%), application-site pain (2.3%), and application-site infection (1.2%). The FDA monograph of crisaborole does not state any requirement for monitoring.

The risks for obtaining skin biopsy samples include a mild amount of pain, bruising, bleeding, or infection at the site of the puncture. Subjects will be instructed in proper wound care to minimize these risks. Subjects may experience scarring at the site of biopsy.

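### The biopsy rule fixes the plaque but not the spot within it, so the single-arm primary endpoint is open to site-selection bias if the baseline site is chosen for thickness

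*Combined protocol and SAP*

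**What the plan says.** Section 4 (Skin punch biopsy of sentinel plaque) says "A sentinel plaque will be selected at baseline" and gives no criterion for choosing it. On location it then says only: "A 4 mm skin punch biopsy will be performed at baseline and at 12 weeks, on the same affected plaque". Nothing in the document sets the position within the plaque, the distance between the two punches, or any mapping of the first site. Photographs are scheduled at baseline and week 12 but are not tied to the biopsy position.

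The same section adds: "If a biopsy has been previously taken of the affected plaque and is available for review, this will be used as the baseline biopsy". For those patients the baseline site was chosen before the study.

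The Summary of Clinical Trial Design states that the primary outcome "is the change in dermal thickness on skin biopsy at 12 weeks". The design is "A Phase 2, pilot, proof-of-concept, open label, single arm prospective study". The dermatopathologist is one "who will be blinded to the study design". Section 10 warns: "Subjects may experience scarring at the site of biopsy". Under Clinical assessment, DIET is scored on the sentinel plaque, and "B-Mode ultrasonographic imaging will be utilized to measure dermal thickness of the sentinel plaque at baseline, week 4, 8 and 12". The document does not say whether the baseline readings come before the punch.

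**The concern.** Morphea plaques need not be equally thick throughout, and the week-12 punch cannot repeat the baseline one. A clinician who wants a clear baseline specimen may naturally take the most indurated point. The later specimen then tends to be thinner even if the drug does nothing. Blinding the pathologist controls the reading of the slide, not where the punch is taken, and with one arm there is no control group in which a site effect would cancel. At stake is a pilot that reports anti-fibrotic activity because of where it sampled. Recruiting 20 rather than 11 does not protect against this, because a fixed bias is more likely to reach significance in a larger sample.

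**Working it through.** **The plan's own figure.** Section 12 gives 11 patients for a 30% change at power 0.80 and alpha 0.05. The Wilcoxon table lists N=11, effect size 1.000, two-sided alpha 0.05, power 0.80310. Take the noncentral-t power for paired differences with effective n = floor(N × 3/π), df = n − 1 and noncentrality = effect size × √n. N=11 gives n=10 and power 0.80310, matching the table; N=10 gives 0.748. The stated sample size is correct on its inputs.

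**Inputs for the check.**
- SD of change: 30 points. This is inferred, since a 30% decrease at effect size 1.0 implies 30/1.0. The table is not labelled in percent.
- Site-to-site SD within a plaque, s: 5, 10 or 15% of thickness. This is an assumption; the documents give no value.
- True drug effect: zero for the false-positive rates. Total SD is held at 30.

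**Size of the spurious shift, choosing between two spots.**
- Thicker of two spots at baseline, random spot at week 12: expected shift = s/√π = 0.564s.
- Thicker spot always identified and punched first, thinner one second: 2s/√π = 1.128s. This is the upper end of the two-spot model. Choosing among more spots raises the shift: simulating the thickest of three, then a random spot, gave 0.843s.

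**False-positive rate at N=20** (n = floor(20 × 3/π) = 19, effect size = shift/30):

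| s | Shift, random later spot | Rejection | Shift, thinner spot later | Rejection |
|---|---|---|---|---|
| 5% | 2.8 | 7% | 5.6 | 12% |
| 10% | 5.6 | 12% | 11.3 | 34% |
| 15% | 8.5 | 21% | 16.9 | 64% |

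A simulation with the exact signed-rank test gives the same figures to within rounding.

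**Effect of N.** A bias of 0.5 SD of the differences (15 points) rejects in 0.293 of trials at N=11 and 0.541 at N=20.

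**If sites are chosen without regard to thickness.** There is then no bias, only noise. Suppose that noise is not already in the 30-point SD. The SD of change becomes √(900 + 2s²), which is 33.2 for s=10 and 36.7 for s=15.
- Power for a true 30-point change at N=11: 0.80 falls to 0.72 and 0.63 by the table's method (0.81 to 0.73 and 0.64 by signed-rank simulation).
- At N=20: 0.98 falls to 0.96 and 0.92.

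**The case against.** The strongest reply is that the protocol nowhere directs the first punch to the thickest spot. A reader might infer that the plan builds bias into the endpoint, but the text does not support that. It permits the bias, and if clinicians ignore thickness the only harm is variance. This reply stands, and it is why the conclusion is conditional.

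The 1.128s figure needs a clinician who identifies the thicker spot without error in every patient and always takes the thinner one later. It is right to treat it as an upper end and to lead with 0.564s. Imperfect identification would lower both.

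The power loss may also be double-counted. The SD in Section 12 rests on archived biopsies, and the document does not show whether it already includes site variation. At the planned 20 patients the loss is small in any case, although drop-outs would reduce that margin. A reader should not infer that the trial is underpowered for this reason.

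It is tempting to add that the biopsy scar distorts DIET and ultrasound in a known direction. The document supports only that scarring may occur. It does not give plaque size, or say that the probe or the score would fall on the scar, and it supplies no direction of effect.

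Finally, in a 20-patient pilot one sentence asking for a recorded, comparable site away from the first punch would close much of the gap. That would improve matters, but it leaves the choice of first site with the clinician; random order takes that choice away.

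**Conclusion.** The concern holds in conditional form. Both punches need only come from one plaque, the two sites must differ, and neither the reader's blinding nor a control arm guards against selective choice of the first site. If that site is chosen for thickness, false-positive rates at N=20 are about 7% to 21% in the milder two-spot case and 12% to 64% at the upper end, for assumed site SDs of 5 to 15%. These figures rest on that assumed range, on a 30-point SD of change inferred from the sample-size table, and on a choice between two spots. The main risk is a false efficacy signal rather than lost power. The stated sample size is not in question. A change is worth making because it is cheap and, where the baseline punch is taken in the study, random order removes selection bias whatever the true within-plaque SD.

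**What to change.** **Section 4, biopsy paragraph.** Before the baseline punch, use the scheduled baseline ultrasound to mark two sites in the sentinel plaque with similar thickness and similar distance from the edge, far enough apart that the first scar does not reach the second. Choose at random which is punched at baseline. Reserve the other for week 12, or for the biopsy taken at drop-out. Record both positions.

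**Reused biopsies.** Where a pre-study biopsy serves as baseline, its site cannot be randomised. Record its position where known, take the later punch at a comparable site away from the scar, flag these patients, and repeat the primary analysis without them.

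**Section 4, Clinical assessment.** State that baseline DIET and ultrasound are done before the punch, and scan at a fixed, mapped site away from both punches.

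**Cost.** A few minutes of mapping at baseline and one allocation list, with no added visit or biopsy. Small plaques may not hold two separated sites; these patients would be flagged.

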## 5. Selection of Subjects:

### Inclusion criteria

Subjects eligible for inclusion in this study must fulfill **all** of the following criteria:

1.  $\geq 18$  years of age
2. Clinical diagnosis of morphea.
3.  $<20\%$  Total body surface area involvement.
4. Does not require systemic immunosuppressive therapy for morphea.
5. No changes (additions, subtractions, or dose modifications) in immunosuppressive systemic therapy 2 months prior to starting the study (hydroxychloroquine, methotrexate, mycophenolate mofetil, azathioprine, cyclosporine, cyclophosphamide, prednisone  $\geq 10$  mg PO daily).
6. No immunomodulating topical therapy (topical steroids or topical calcineurin inhibitor), and no topical vitamin D analogue, 2 weeks prior to starting study.
7. No allergy to crisaborole or vehicle.
8. No known renal disease
9. Able to give informed consent.

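### An available earlier biopsy of the plaque, whatever its age, must serve as baseline, so the primary 12-week change can include an unknown period before treatment

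*Combined protocol and SAP*

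**What the plan says.** Section 4 (Skin punch biopsy of sentinel plaque) sets the default: "A 4 mm skin punch biopsy will be performed at baseline and at 12 weeks, on the same affected plaque". It then makes an exception: "If a biopsy has been previously taken of the affected plaque and is available for review, this will be used as the baseline biopsy". The wording is mandatory and availability is the only condition. Neither this section nor any other limits the specimen's age, sets a condition on treatment received since, or asks for its date.

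The endpoint is tied to the treatment period. Section 2 compares dermal thickness and fibrosis "as measured by histology at baseline and after 12 weeks of crisaborole 2% ointment". The Summary of Clinical Trial Design defines the primary outcome as "the change in dermal thickness on skin biopsy at 12 weeks". Section 12 anticipates a 30% decrease over the same 12 weeks. The trial is an "open label, single arm prospective study".

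Section 5 contains two medication windows. Criterion 5 reads "No changes (additions, subtractions, or dose modifications) in immunosuppressive systemic therapy 2 months prior to starting the study"; criterion 6 reads "No immunomodulating topical therapy (topical steroids or topical calcineurin inhibitor), and no topical vitamin D analogue, 2 weeks prior to starting study". Both count back from study start.

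**The concern.** For a patient with a fresh baseline, the measured change covers the 12 weeks of treatment. For a patient with an archived baseline, it covers the time from that earlier biopsy to study start plus the 12 weeks. A patient could be biopsied, receive a full course of a topical steroid, wash out for 2 weeks and enrol without breaking any rule. Any change in the plaque over that time would enter the primary outcome.

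If earlier changes run mainly one way, the primary estimate is shifted. Earlier thinning would be credited to crisaborole, and earlier thickening would hide a true effect. With no control arm, nothing in the primary analysis can subtract it. Blinded histology does not help, because a change that really happened before treatment is still there when the slide is read blind.

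**Working it through.** **1. The plan's own figure.** The table in Section 12 gives power 0.80310 for N = 11 at effect size 1.000, two-sided alpha 0.05. It is reproduced by the noncentral-t power of a paired t-test with the number of pairs reduced to floor(3N/π):

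- N = 11: floor(10.50) = 10 pairs, noncentrality 1.0 × √10 = 3.16, power 0.80310.
- N = 12: floor(11.46) = 11 pairs, power 0.84753, also as in the table.
- N = 20: floor(19.10) = 19 pairs, power 0.98447.

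The sample-size arithmetic is not in dispute.

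**2. SD of the change.** Section 12 links N = 11 to a 30% change, and the N = 11 rows have effect size 1.0. Since effect size = mean change / SD, the implied SD is 30% / 1.0 = 30% of baseline. Earlier changes of 10%, 20% and 30% are then 1/3, 2/3 and 1 SD.

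**3. Assumed inputs.** The documents do not give the number of archived baselines (k) or the earlier change (d). I take k = 2, 5 or 10 of 20 pairs and d = 10%, 20% or 30%. Each archived pair receives a fixed shift and keeps the same SD as a fresh pair, which is a simplification.

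**4. Shift in the mean.** Shift = (number thinned − number thickened) / 20 × d. For example, 5 archived and all thinned by 20% gives 5/20 × 20 = 5 percentage points. Ten archived, split 5 and 5, gives 0.

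**5. False-positive rate, no drug effect.** Exact two-sided signed-rank test at 0.05 (N = 20: critical W = 52, exact size 0.0484), 400,000 simulated trials per cell:

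| Archived baselines | Mean shift at d = 30% | d = 10% | d = 20% | d = 30% |
|---|---|---|---|---|
| 2, all thinned | 3 points | 0.049 | 0.053 | 0.057 |
| 5, all thinned | 7.5 points | 0.059 | 0.090 | 0.132 |
| 10, all thinned | 15 points | 0.099 | 0.244 | 0.442 |
| 10, 8 thinned and 2 thickened | 9 points | 0.063 | 0.098 | 0.140 |
| 10, 7 thinned and 3 thickened | 6 points | 0.052 | 0.058 | 0.063 |
| 10, 5 thinned and 5 thickened | 0 points | 0.043 | 0.030 | 0.017 |

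**6. Power for a true 30% decrease, archived pairs kept or removed.** Same test; with no archived baselines the power is 0.985.

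| Archived baselines | Kept: d = 10%, 20%, 30% | Removed |
|---|---|---|
| 2, all thickened | 0.979, 0.968, 0.953 | 0.973 (18 pairs) |
| 5, all thickened | 0.964, 0.919, 0.830 | 0.938 (15 pairs) |
| 10, all thickened | 0.927, 0.751, 0.442 | 0.784 (10 pairs) |
| 10, 5 thinned and 5 thickened | 0.982, 0.973, 0.950 | 0.784 (10 pairs) |

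The exact test size after removal is 0.0483, 0.0479 and 0.0488 with 18, 15 and 10 pairs. The table's own method, which rounds the pairs down, gives slightly lower power: 0.972, 0.932 and 0.748.

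**The case against.** The case for leaving the rule alone has several parts.

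- **Exposure may be small.** Entry needs only a clinical diagnosis, the sentinel plaque is chosen at baseline with no instruction to pick one already biopsied, and the specimen must be available. With 2 archived baselines the test is practically at its nominal level. This stands: the larger figures rest on assumed shares.
- **The weakness is not new.** A single-arm trial cannot separate natural course from drug effect even with fresh baselines. This also stands. The rule lengthens the uncontrolled interval by an unknown amount; it does not create it.
- **There is a good reason for the rule, and there is other evidence.** Reusing tissue spares a punch, and Section 10 warns: "Subjects may experience scarring at the site of biopsy". Ultrasound thickness of the same plaque is taken at the actual baseline visit. It could expose a discordant result, but it is secondary and does not correct the primary outcome.
- **Removing older pairs can do harm.** If earlier changes were balanced, dropping 10 pairs costs power and corrects nothing.

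A reader might go further and infer that the rule favours crisaborole, or that the false-positive rate is 44%. The documents support neither. They give no direction of earlier change, and 44% needs half the sample archived and every one of those plaques thinned by as much as the drug is hoped to achieve. A reader might also infer that an age limit would free the result of bias, or that specimen dates would show which way plaques had moved. Neither follows. A specimen inside the limit can still predate a change, and dates and counts show exposure, not direction.

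**Conclusion.** The concern holds and should be fixed. Followed as written, the rule lets the primary change cover more than the 12 weeks that Sections 2, 4 and 12 attach to it, for an unknown number of patients and an unknown length of time. Its effect ranges from negligible (2 archived baselines, or balanced earlier changes) to serious (many archived baselines moving one way). The documents do not allow a choice between these cases, and the plan does not collect even the exposure. The sizes rest on an SD of 30% of baseline inferred from the sample-size table, 20 complete pairs, and assumed shares and shifts.

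**What to change.** In Section 4 (Skin punch biopsy of sentinel plaque):

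1. State a maximum specimen age before first application for the primary paired test, chosen and justified by the sponsor. The 2 months in criterion 5 is only an example; nothing in the documents links it to dermal thickness.
2. Record the date of every baseline specimen, and report how many were archived and how old they were.
3. Report the all-pairs result, including older specimens, as a sensitivity analysis.
4. Compare the ultrasound change from the actual baseline visit between patients with archived and fresh baselines.
5. Keep patients with older specimens in the ultrasound, DIET, LoSCAT and Skindex-29 analyses.
6. State whether the default baseline punch applies to patients whose earlier specimen is too old.

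**Gain.** The limit reduces pre-treatment change without removing it. The false-positive rate returns to 4.8–4.9% only if the retained specimens carry no earlier change; ten retained specimens that had thinned by 10% would still give about 10%. Power can also rise: with 10 archived baselines all thickened by 30%, from 0.44 to 0.78.

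**Cost.** A short amendment; the limit itself adds no biopsy. If the sponsor decides that the default punch applies, no pairs are lost on this account, but each of these patients has one more punch with the risks in Section 10. If not, their pairs enter only the sensitivity analysis. With 10 archived baselines and balanced earlier changes, power then falls from 0.95–0.98 to 0.78. Up to 20 − 11 = 9 pairs can be lost to this rule and drop-out combined before the number falls below the planned 11.

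### An exit biopsy is planned for patients who leave for progression or adverse effects, but no DIET, LoSCAT, Skindex-29 or ultrasound is scheduled then, so the week 12 secondary results lean towards patients who stayed

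*Combined protocol and SAP*

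**What the plan says.** **Exit procedure.** Section 4, under the skin punch biopsy heading, states: "Patients who drop out of the study because of progression of their disease or adverse effects will undergo a skin punch biopsy". The biopsy is timed at drop-out. No other assessment is named for that contact.

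**Schedule of the secondary measures.** Section 4, Clinical assessment, states: "Patients will have a clinical assessment at baseline and at weeks 4, 8 and 12". It adds: "Physician and patient reported assessment and skin imaging will be performed at baseline, week 4, 8 and 12, and at week 20". The week 20 visit is not assured: "An optional post treatment follow-up will be performed at week 20". The table in the Summary of Clinical Trial Design follows the same schedule and has no early-exit column.

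**Outcomes.** The primary outcome "is the change in dermal thickness on skin biopsy at 12 weeks". The secondary outcomes are fixed at set weeks, for example "Change in DIET score of sentinel plaque at 4, 8 and 12 weeks" and "Change in LoSCAT score at 4, 8 and 12 weeks". Skindex-29 and ultrasound dermal thickness have the same three time points.

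**Analysis.** Section 12 covers the sample size for histologic dermal thickness. Drop-outs appear there only as a reason to recruit 20 patients when 11 are needed. It gives no analysis population, missing-data rule or method for the secondary outcomes. No section says that patients who stop are followed to week 12.

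**The concern.** Progression is one of the plan's own named reasons for leaving, so whether a score is missing can depend on what the score would have shown. DIET grades the sentinel plaque and LoSCAT grades disease overall; a worsening that makes a patient leave is what these tools are there to record. The exit biopsy cannot stand in for them. It samples one plaque, whereas spread elsewhere would show in LoSCAT and not in that specimen.

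The trial is open label with a single arm, and every secondary outcome is judged against the patient's own baseline. No control group loses patients in a comparable way. If those who worsened drop out of the week 12 figures, the average change moves towards improvement. Comparing physician and patient reported outcomes over time is the second stated purpose in Section 2, so the loss touches a declared aim. Scores that were not taken cannot be recovered by analysis.

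**Working it through.** **1. The plan's own figure.** Section 12 gives power 0.80310 for a two-sided paired Wilcoxon test with N = 11, effect size 1.0 and alpha 0.05. With the usual efficiency factor for normal data, effective n = floor(11 × 3/π) = floor(10.50) = 10. A noncentral t calculation with 9 degrees of freedom and noncentrality 1.0 × √10 = 3.16 gives power 0.8031, so the figure reproduces. The margin is 20 − 11 = 9 patients, or 9/20 = 45%. It protects power for the histologic outcome. It does nothing about bias when the reason for leaving is related to outcome.

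**2. What is lost, by time of exit.** These follow from setting the exit sentence beside the schedule.

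| Time of exit | Secondary measures on file | Scheduled values missing |
|---|---|---|
| Before week 4 | baseline | weeks 4, 8, 12 |
| At the week 4 visit | baseline, week 4 (taken that day) | weeks 8, 12 |
| Between weeks 4 and 8 | baseline, week 4 | weeks 8, 12 |
| At the week 8 visit | baseline, weeks 4, 8 (taken that day) | week 12 |
| Between weeks 8 and 12 | baseline, weeks 4, 8 | week 12 |

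Every early exit loses week 12. Weeks 4 and 8 are affected in part. Scores at the point of exit are unassured in the three between-visit rows and already covered in the two at-visit rows.

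**3. Size, as an illustration.** The documents give enrolment of 20. They give no drop-out rate, no mix of reasons and no spread for the secondary outcomes, so the following are assumptions: completers improve by d; k patients leave for the named reasons; leavers change by w·d, with w = 0 (no change) or w = −1 (worsening equal to the completers' improvement).

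All-patient mean = [(20 − k)·d + k·w·d]/20. Overstatement = d divided by that mean.

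| k | Mean, w = 0 | Overstatement | Mean, w = −1 | Overstatement |
|---|---|---|---|---|
| 2 | 18d/20 = 0.90d | 1.11 | (18 − 2)d/20 = 0.80d | 1.25 |
| 3 | 17d/20 = 0.85d | 1.18 | (17 − 3)d/20 = 0.70d | 1.43 |
| 4 | 16d/20 = 0.80d | 1.25 | (16 − 4)d/20 = 0.60d | 1.67 |

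The absolute gap is (k/20)(1 − w)d. It is positive whenever leavers do worse than completers (w below 1), so the direction does not depend on the particular values chosen.

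**The case against.** The strongest reply is that the gap is narrower than it looks, and much of that reply stands.

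- A reader might infer that leavers get a biopsy and nothing else. The sentence sits in a subsection about biopsies, and nothing in the plan forbids scoring at exit. What the text supports is that exit scoring is not specified, and so is not assured for any patient.
- A reader might infer that the worsened score is never recorded. That fails when the decision to leave is made at the week 4 or week 8 visit, where all four measures are taken. The gap at the point of worsening concerns exits between visits.
- A reader might infer that a completers' analysis is planned. No analysis population is stated for the secondary outcomes. Resting mainly on those who stayed is the default result of missing values, and patients who leave later still contribute their earlier visits.
- A reader might take the margin of 9 losses as the expected drop-out and compute a far larger distortion. If 9 of 20 left and all worsened by exactly d, the mean would be (11 − 9)d/20 = 0.1d and the overstatement 10 times. The documents do not support this. They state no expected drop-out, the exit sentence also covers adverse effects, where the skin need not have worsened, and the ratio is large because the assumed mean almost cancels. With no change in the same 9 patients it would be 20/11 = 1.82.

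It is also fair that the exit biopsy partly protects the primary outcome, and that these are secondary measures in a 20-patient pilot. None of this supplies the missing exit scores. A team following the written schedule would have no instruction to take them at a contact where the patient is already being biopsied.

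**Conclusion.** The concern holds in a limited form. For patients who leave because of progression or adverse effects, the plan specifies histology at exit and leaves the four secondary measures unspecified. The exposure is full at week 12 and partial at weeks 4 and 8. Scores at the point of worsening are at risk when exit falls between scheduled visits.

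The direction, towards apparent improvement, rests on one assumption: that leavers do worse on average than completers. The size cannot be derived from the documents. With 2 to 4 of 20 leaving, the illustrative overstatement is about 1.1 to 1.25 times if leavers do not change, and about 1.25 to 1.7 times if they worsen as much as completers improve. The point is worth correcting because the loss is irreversible and the remedy cheap. It does not undermine the primary outcome or the sample size.

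**What to change.** **Collection.** Add an early-exit column to the table in the Summary of Clinical Trial Design, and one sentence to the biopsy subsection of Section 4: DIET, LoSCAT, Skindex-29, ultrasound and photography are done at the exit visit before the biopsy, unless already done at a scheduled visit that day. The order matters because the biopsy disturbs the plaque being scored and imaged.

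**Reporting.** Add a sentence to Section 12. Exit values are listed with the week of exit and shown in a sensitivity summary alongside the week 12 results of patients who completed. They are not entered as week 12 values: a score from another week is a different quantity, and carrying it forward would be a further assumption.

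**Cost.** One column, two sentences and about half an hour more at that visit (assumed). The patient is already attending for the biopsy, and the measures are those used at the scheduled visits. Treatment and sample size do not change. The change does not reach patients who leave for other reasons, whose week 12 values would still be missing; their number and reasons should be reported.
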